5.5 Data Analysis and Statistical Considerations

[figure not shown]
A maximum of 12 patients will be treated with PVSRIPO, and then carefully monitored for safety for at least a year after treatment. Of particular interest will be the incidence of adverse events that occur during the first 14 days after PVSRIPO treatment and the inflammatory events that occur during the first year after PVSRIPO treatment. Our experience with PVSRIPO treatment of adult patients with recurrent WHO grade IV malignant glioma suggests that a patient remains at risk, during the first 12 months post-PVSRIPO treatment, of demonstrating neurologic or radiographic signs suggestive of an inflammatory reaction secondary to the immune response triggered by PVSRIPO that requires a dose of dexamethasone above 4 mg a day. As described in Section [9.1.6](#), such patients will be treated with bevacizumab 7.5 mg/kg IV every 3 weeks if possible, or alternatively corticosteroids or surgery.

The accrual of pediatric patients to this study was staggered for the first 5 patients enrolled so that no more than 1 patient was treated every 14 days. A slow accrual was planned to minimize the number of pediatric patients exposed to PVSRIPO before adequate information about the sequelae of the inflammatory process within a pediatric patient is known. Based on a review of the available safety data and acceptable tolerability in the first 5 patients treated with PVSRIPO (no dose-limiting toxicities or suspected unexpected serious adverse reactions observed), the protocol was amended to allow for accrual of subsequent patients without the 14-day waiting period in Protocol Amendment 12.

Two sets of safety monitoring guidelines are proposed in Section [15.4.1](#), with one focused on acute toxicity (i.e. occurring during the first 14 days after PVSRIPO administration), and one focused on long-term issues.

The Kaplan-Meier estimator will describe the survival of patients treated with PVSRIPO. Survival (OS) will be calculated as the time between PVSRIPO infusion and death, or last follow-up if the patient remains alive. Analyses will be stratified by grade.

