9.1.5 Definition of Unacceptable Toxicity

Toxicities will be graded according to the NCI CTCAE version 4 criteria. Any Grade 3 or any Grade 4 toxicity that is not reversible within 2 weeks, any life-threatening event deemed related to the study drug, or any treatment-related death will be considered unacceptable.

Any Grade 2 or higher autoimmune toxicities, particularly those affecting vital organs (e.g. cardiac, renal, CNS), will be considered an unacceptable toxicity, if it occurs within 2 weeks post-infusion. Grade 3 or higher surgical complications from insertion of the catheter are considered an unacceptable toxicity.

Exceptions to these unacceptable toxicities are as follows:

- Events associated with the biopsy procedure/catheter placement: Seizures or hemorrhages occurring during anesthesia or the biopsy/catheter insertion proper prior to administration of the agent if Grade 2 or lower.
- Seizures: Due to the nature of the disease under investigation in this protocol, patients may have pre-existing seizures or be susceptible to new seizures as a result of the underlying disease process. Although seizures may be defined as Grade 3 or 4 toxicities under NCI CTC, and will be reported as such in this protocol, seizures will not be considered an unacceptable toxicity if, in the opinion of the site Principal Investigator they have not increased in frequency or can be attributed to another recognized cause of increasing seizure frequency such as sub-therapeutic anti-convulsant levels or biopsy proven tumor progression.
- New or worsening neurologic deficits: Due to the nature of the disease under investigation in this protocol, patients may have an increase in pre-existing neurologic deficits or may develop new neurologic deficits as a result of tumor invasion. A new neurologic deficit, which resolves within 2 weeks after initiation of medical therapy, will not be considered an unacceptable toxicity. New neurological symptoms will not be an unacceptable toxicity if they can be ascribed to tumor progression (e.g. documented with histopathologic analyses of biopsy tissue), or they respond to treatment (e.g. oral steroids) within 2 weeks.

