15.4.1 Overview of Study Design and Monitoring

Patients will be treated with PVSRIPO, then carefully monitored for safety for at least 1 year after treatment. Of particular interest will be the incidence of AEs that occur during the first 14 days after PVSRIPO treatment and the inflammatory events that occur during the first year after PVSRIPO treatment. The experience with PVSRIPO treatment of adult patients with recurrent WHO grade IV malignant glioma suggests that a patient remains at risk, during the first 12 months post-PVSRIPO treatment, of demonstrating neurologic or radiographic signs suggestive of an inflammatory reaction secondary to the immune response triggered by PVSRIPO that requires a dose of dexamethasone above 4 mg a day. As described in Section 9.1.6, such patients will be treated with bevacizumab 7.5 mg/kg IV every 3 weeks if possible, or alternatively corticosteroids or surgery.

Two sets of safety monitoring guidelines are proposed, with one focused on acute toxicity (i.e. occurring during the first 14 days after PVSRIPO administration), and one focused on long-term issues.

Acute Toxicity Monitoring Guidelines: Monitoring rules based upon the occurrence of an unacceptable toxicity, as defined in Section 9.1.5, during the first 14 days after PVSRIPO administration are shown below in **Table 4**.

If the number of patients with an unacceptable toxicity surpasses the noted thresholds, accrual will be suspended. Data will be carefully reviewed to determine if accrual should be terminated, continued without modification, or continued with appropriate modification (e.g. PVSRIPO dose reduction).

Table 4. Acute Toxicity Monitoring Rules.

# of Patients Accrued	Accrual Suspension Threshold
0 – 6	≥2 patients with unacceptable toxicity
7-9	≥3 patients with unacceptable toxicity
10-12	≥4 patients with unacceptable toxicity

The probability of study suspension and the expected number of treated patients before study suspension is tabulated below in **Table 5** as a function of the true underlying probability of an unacceptable toxicity.

Table 5. Probability of study suspension.

True Underlying Probability of a Unacceptable Toxicity within 14 days of PVSRIPO administration	Probability of Accrual Suspension	Expected Number of Patients to be Accrued
0.05	0.030	11.8
0.10	0.124	11.1
0.15	0.262	10.2
0.20	0.411	9.2
0.25	0.560	8.1
0.30	0.681	7.2
0.35	0.792	6.2
0.40	0.873	5.4

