Long-term Monitoring: If any patient experiences an inflammatory reaction that does not improve within 18 weeks of commencing bevacizumab or steroid treatment, the inflammatory reaction will be considered “irreversible.” If a patient experiences “irreversible” inflammatory reaction, further enrollment of patients on the PVSRIPO trial will be temporarily interrupted and data on all previously treated patients will be carefully reviewed to determine if the study needs modification. Options may include dose reductions in future patients (next PVSRIPO dose would be 3.3×10^6 TCID50), modification of the approach to treating a patient with an inflammatory reaction, study termination, or accrual continuation without modification.

The FDA and/or the DSMB for this study may be part of this decision-making in the event that there are unacceptable toxicities or inflammatory issues.

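### A single treatment-related death or related life-threatening event within 14 days does not by itself mandate suspension of accrual, whereas one irreversible inflammatory reaction does interrupt enrollment

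*Combined protocol and SAP*

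**What the plan says.** Section 9.1.5 defines one class of unacceptable toxicity. It contains Grade 3 or 4 toxicity that does not reverse in two weeks, early autoimmune toxicity from Grade 2 upward and catheter-insertion complications from Grade 3 upward. It also says that "any life-threatening event deemed related to the study drug, or any treatment-related death will be considered unacceptable". No member of the class has a consequence of its own.

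Section 15.4.1 introduces Table 4 as "Monitoring rules based upon the occurrence of an unacceptable toxicity, as defined in Section 9.1.5, during the first 14 days after PVSRIPO administration". The thresholds are:

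- up to 6 patients accrued: "≥2 patients with unacceptable toxicity"
- 7 to 9 accrued: "≥3 patients with unacceptable toxicity"
- 10 to 12 accrued: "≥4 patients with unacceptable toxicity"

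Suspension leads to a data review that may end accrual, continue it unchanged, or continue it with changes. Section 15.8 (Interim Analysis) only points back to 15.4.1.

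The long-term rule in 15.4.1 works differently. One reaction that has not improved 18 weeks after bevacizumab or steroids were started is called irreversible, and then "further enrollment of patients on the PVSRIPO trial will be temporarily interrupted" while the data are reviewed.

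Section 5.5 adds that, after the first five patients, "the protocol was amended to allow for accrual of subsequent patients without the 14-day waiting period".

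**The concern.** The acute rule counts patients and ignores severity. A drug-related death adds one to the same tally as a Grade 2 autoimmune event, and a tally of one is below every threshold in Table 4. The long-term rule cannot fill the gap, because a death inside 14 days can never meet an 18-week definition. The most severe acute outcome therefore has a looser written trigger than a delayed reaction that the child may survive.

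At stake is whether the next child is treated before anyone is obliged to stop and look. The 14-day spacing used to give a built-in pause and has been lifted for patient 6 onward. Section 9.1.6 acknowledges that the virus could in principle damage motor neurons, with respiratory failure among the possible results.

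**Working it through.** **Inputs.** Thresholds 2, 3 and 4 for patients 1–6, 7–9 and 10–12 (Table 4); maximum 12 patients (Section 15.9). The per-child rate p of a fatal or related life-threatening event is not in the documents, so 1%, 2%, 5% and 10% are assumed, with no other unacceptable toxicity. Each patient's outcome is taken as known before the next is treated.

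**Step 1: reproduce Table 5.** Add patients one at a time, count each unacceptable toxicity as one, and stop when the count reaches the threshold.

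| True rate | Table 5 suspension | Exact | Table 5 expected N | Exact |
|---|---|---|---|---|
| 0.05 | 0.030 | 0.035 | 11.8 | 11.75 |
| 0.10 | 0.124 | 0.128 | 11.1 | 11.11 |
| 0.20 | 0.411 | 0.408 | 9.2 | 9.19 |
| 0.30 | 0.681 | 0.686 | 7.2 | 7.15 |
| 0.40 | 0.873 | 0.872 | 5.4 | 5.45 |

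Hand check at 0.05: two or more events in the first six has probability 1 − 0.95^6 − 6(0.05)(0.95^5) = 0.0328. First suspension at patients 8–9 adds 0.0018 and at 11–12 adds 0.0003, giving 0.0349. All eight rows of Table 5 agree within about half a percentage point, so Table 5 assumes a check after each patient and no separate trigger for death.

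The text says "If the number of patients with an unacceptable toxicity surpasses the noted thresholds, accrual will be suspended". Read literally, that needs one more event than the table shows and gives 0.003 to 0.655 across the eight rates. This does not match Table 5, so the thresholds as tabulated are meant.

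**Step 2: 12 patients.** P(at least one) = 1 − (1 − p)^12. Subtracting the suspension probability gives the chance of an event with no mandated pause.

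| p | At least one | Table 4 suspends | Event, no mandated suspension |
|---|---|---|---|
| 0.01 | 0.114 | 0.0015 | 0.11 |
| 0.02 | 0.215 | 0.006 | 0.21 |
| 0.05 | 0.460 | 0.035 | 0.425 |
| 0.10 | 0.718 | 0.128 | 0.59 |

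**Step 3: patients 6–12.** Section 5.5 reports no dose-limiting toxicity in the first five. Assume this means no unacceptable toxicity under 9.1.5. Suspension then needs at least 3 events in patients 6–9, or at least 4 by patient 12. At p = 0.10 the first route is 4(0.1^3)(0.9) + 0.1^4 = 0.0037 and the second adds 0.0017, in total 0.005. P(at least one) = 1 − (1 − p)^7.

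| p | At least one | Table 4 suspends | Event, no mandated suspension |
|---|---|---|---|
| 0.01 | 0.068 | <0.0001 | 0.07 |
| 0.02 | 0.132 | <0.0001 | 0.13 |
| 0.05 | 0.302 | 0.0006 | 0.30 |
| 0.10 | 0.522 | 0.005 | 0.52 |

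Events in both patients 6 and 7 would make 2 of 7, still below the threshold of 3.

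**Step 4: children treated after a first event, p = 0.05.** Take the expected number treated minus the expected position of the first event (or the last patient if there is none), and divide by P(at least one).

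- Fresh 12: the expected position is (1 − 0.95^12)/0.05 = 9.19. Then 11.75 − 9.19 = 2.56, and 2.56/0.460 = 5.6.
- Patients 6–12: the expected position within the seven is (1 − 0.95^7)/0.05 = 6.03. Then 6.998 − 6.03 = 0.965, and 0.965/0.302 = 3.2.

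Both are conditional on an event. Averaged over all trials they are 2.6 and about 1.0.

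**The case against.** The strongest reply is that this is a design choice. Table 4 does what it sets out to do, Table 5 reproduces, and nothing in 15.4.1 contradicts itself. That stands. The long-term trigger is also not odd in itself: peri-tumoral inflammation is the main toxicity attributed to the agent (Section 7.3), and edema that resists treatment can leave permanent deficits (Section 9.1.6).

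A reader might infer that accrual must go on after a death, or that the next child could be treated with nobody alerted. The documents do not support either reading. Section 15.4.1 calls its rules guidelines, and they bar no earlier pause. A death that brings the tally to the threshold does suspend accrual. The DSMB-Plus can recommend stopping enrollment (13.7), the PI-sponsor can end the study at will (9.5), and the FDA or DSMB may be drawn in (15.4.1). Section 13.2.1 requires SAE reports to the sponsor within 24 hours, certain deaths to the IRB within 24 hours, and unexpected fatal or life-threatening suspected reactions to the FDA within 7 days. The DSMB-Plus charter was not available and may contain a pause rule.

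What remains is that none of these routes, as written in the protocol, halts accrual. The same routes were open for irreversible inflammation, and the authors still wrote a mandatory interruption there.

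The rates are also open to challenge. They are assumptions, and 5% or 10% may be high for related deaths and life-threatening events, so the 1% and 2% rows belong beside them. The 12-patient figures overstate exposure under the current amendment, where seven patients remain if five have been treated.

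**Conclusion.** The point holds for the written rule: one treatment-related death or related life-threatening event within 14 days does not by itself mandate suspension, at any stage from patient 1 to 12. Over the assumed rates of 1% to 10%, an event with no mandated suspension has probability 0.11 to 0.59 across 12 patients. For patients 6–12 it is 0.07 to 0.52, with Table 4 suspending in at most about 0.5% of trials.

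These figures rest on the assumed rates, on no other unacceptable toxicity occurring, on five clean patients in the second set, and on outcomes being known before the next infusion. With the spacing lifted, that last condition may fail, and then neither the present rule nor a single-event rule could hold back a child already treated.

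A reader might infer that Table 4 or Table 5 is wrong. Neither is. The gap lies between the acute and long-term rules and should be fixed as a cheap safety improvement.

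**What to change.** Bring the acute rule into line with the single-event long-term rule. Add to 15.4.1 that any single treatment-related death, or life-threatening event deemed related to the study drug, within 14 days of infusion suspends accrual for the review already described there, whatever the Table 4 count. Keep Table 4 for all other unacceptable toxicities. Recompute Table 5 with the assumed share of fatal or life-threatening events stated. If the DSMB-Plus charter already has such a rule, cite it in 15.4.1.

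The cost is one sentence, a new Table 5 and more pauses. At 10% total toxicity, of which 2 points are fatal or life-threatening, suspension rises from 0.13 to 0.28 over 12 patients and from 0.005 to 0.13 over patients 6–12. If half of that 10% qualifies, the 12-patient figure is 0.48. Each pause leads only to a review, which may resume accrual unchanged.

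The added sentence would not reach permanent paralysis that is not life-threatening, which would stay one ordinary Table 4 event. The sponsor should decide and state whether that is intended.

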15.4.2 Primary Objective Analyses

Percentage of patients that experience unacceptable toxicity during the 14-day period post-PVSRIPO treatment will be calculated.

The proportion of patients who require low-dose bevacizumab or steroid treatment due to an inflammatory reaction secondary to an immune response to PVSRIPO treatment will be calculated. In addition, the time to initiation of such treatment will be calculated and summarized using Kaplan-Meier methodology.

Adverse events experienced by protocol subjects from the time of catheter placement will be summarized in several forms to satisfy scientific and monitoring needs, as well as various regulatory reporting needs (e.g. FDA, DCI SOC, and ClinicalTrials.gov). These include a summary of the frequency of adverse events that are possibly, probably, or definitely related to protocol treatment tabulated by the maximum grade for each type of adverse event, as well as a summary of the frequency of adverse events regardless of attribution tabulated by the maximum grade for each type of adverse event.

15.5 Secondary Objective

The secondary objective is the estimation of overall survival (OS), which will be calculated as the time between PVSRIPO infusion and death, or last follow-up if the patient remains alive. The Kaplan-Meier estimator will be used to describe the survival of patients treated with PVSRIPO. Median OS will be estimated, as well as 6-, 12-, and 24-month OS. Analyses will be stratified by histologic grade.

15.6 Exploratory Objective

An exploratory objective of this study is to describe changes visualized on imaging due to intratumoral inoculation of PVSRIPO. Two components of the inflammatory reaction will be characterized: the enhancing lesion and the edema (FLAIR) area. Given that imaging following immunotherapy differs greatly from what is typically seen following chemoradiation treatment or treatment with anti-angiogenic compounds, evaluation of response using with Macdonald criteria or RANO criteria is not appropriate in this trial. Immunotherapy can trigger an inflammatory immune response that is observed on imaging. Distinguishing between the inflammatory immune response and progressive disease is difficult. Therefore, an exploratory objective of this study is to describe radiographic imaging post-PVSRIPO treatment.

15.7 Other Exploratory Objectives

An additional exploratory objective is to describe changes in tumor volume based upon imaging. Subjects' MRIs will be followed for changes in tumor volume post-PVSRIPO treatment. Another exploratory objective is the assessment of immunologic changes stemming from the administration of PVSRIPO treatment. Peripheral blood will be collected at defined intervals for correlative immune monitoring studies in serum and in peripheral blood monocytes. These include (i) analyses of innate and inflammatory immune events (HMGB1, inflammatory cytokines, NK and NKT-cells and regulatory immune subsets (Tregs & MDSCs)); (ii) analyses of adaptive immune responses (lineage, maturation, induction and activation/functional status of tumor antigen-specific T-cells). A final exploratory objective is to identify genetic predictors of response or failure of response to treatment with PVSRIPO. The Cox model will explore the impact of genetic markers of survival time. With logistic regression, the association between genetic markers and being a long-term survivor will be explored.

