8 OBJECTIVES AND ENDPOINTS

Table 1. Objectives and Endpoints

	Objective	Endpoint	Analysis
Primary	Confirm the safety of the selected dose of PVSRIPO when delivered intracerebrally by convection-enhanced delivery (CED) in children with recurrent Grade III or IV MG	Percentage of patients that experience unacceptable toxicity during the 14-day period post-PVSRIPO treatment. Proportion of patients who require low-dose bevacizumab or steroid treatment due to an inflammatory reaction secondary to an immune response to PVSRIPO treatment will be calculated.	See Section 15.4
Secondary	Estimate Overall Survival (OS) in children with recurrent WHO Grade III and IV malignant glioma treated with a single dose of PVSRIPO	Proportion of patients alive 2 years after PVSRIPO treatment	See Section 15.5

Exploratory	Describe changes visualized on imaging due to intratumoral inoculation of PVSRIPO	Description of imaging changes	See Section 15.6
Other Exploratory	Describe changes in tumor volume visualized on imaging after intratumoral inoculation of PVSRIPO	Change from baseline in tumor volume based on imaging	See Section 15.7
Other Exploratory	Assess immunologic responses in peripheral blood and in serum	Change from baseline in immune function	See Section 15.7
Other Exploratory	Identify genetic predictors of response or failure of response to treatment with PVSRIPO	Identification of genetic markers as predictors of response	See Section 15.7

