9.1.4 Biopsy Sampling and Analyses

Biopsy material will be obtained from tumor tissue prior to virus administration. This tissue material will be subjected to routine histology to confirm tumor recurrence by the study neuropathologist, Dr. [name] or his designate.

Molecular genetic tests will also be conducted on extracts of tumor cells from the protocol-specified biopsy prior to PVSRIPO infusion. After acquiring sufficient tissue for standard clinical pathologic testing, up to three additional core biopsies will be obtained, if possible. These additional core biopsies will be frozen in optimal cutting temperature (OCT) fixative and kept at liquid nitrogen temperature. They will be used for genetic analysis, including full genome or full exome sequencing as well as other molecular genetic testing. The goal of these molecular genetic tests is to identify genetic predictors of response or failure of response to treatment with PVSRIPO. The molecular genetic testing will include, but is not limited to, DNA sequencing, gene amplification, and gene expression.

The goal of these molecular genetic tests is to identify genetic predictors of response or failure of response to treatment with PVSRIPO. The amount of tissue required for this testing should be sufficient to yield a minimum of one microgram of DNA.

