12.7.3 Radiographic Review

A CT will be obtained to confirm catheter placement prior to beginning the PVSRIPO infusion. A MRI of the brain without gadolinium enhancement will be obtained within 4 hours of

completing the PVSRIPO infusion to monitor distribution of the infusion. A MRI of the brain with gadolinium enhancement will be obtained at all subsequent visits.

Given that imaging following immunotherapy differs greatly from what is typically seen following chemoradiation treatment or treatment with anti-angiogenic compounds, evaluation of response using with Macdonald criteria or RANO criteria is not appropriate in this trial. Immunotherapy can trigger an inflammatory immune response that is observed on imaging. Distinguishing between the inflammatory immune response and progressive disease is difficult. Therefore, an exploratory objective of this study is to describe radiographic imaging post-PVSRIPO treatment. Another exploratory objective of this study is to describe changes in tumor volume based upon radiographic imaging. For that reason, subjects who have gone off study may continue to be followed for collection of MRI measurements. For the purpose of this objective, relative tumor volume is estimated from the MRI using the metric of multiplying the widest tumor diameter with the perpendicular height of the tumor in that same slice.

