15.1 Analysis Sets

All patients who receive PVSRIPO treatment will be included in all safety and efficacy analyses.

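### The marker endpoint is named as predictors of response to PVSRIPO, but response is not defined and the planned analyses can show only an association with survival after treatment

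*Combined protocol and SAP*

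**What the plan says.** **The aim.** Table 1 (Section 8) names the endpoint as "Identification of genetic markers as predictors of response". Section 9.1.4 states: "The goal of these molecular genetic tests is to identify genetic predictors of response or failure of response to treatment with PVSRIPO". Sections 5.1 and 15.7 carry the same objective.

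**Response.** Section 12.7.3 says that "evaluation of response using with Macdonald criteria or RANO criteria is not appropriate in this trial", and 15.6 repeats this. Both add that inflammation and progression are hard to tell apart on imaging. CR, PR and ORR appear only in the abbreviation list. Section 12.7.3 does supply an imaging measure: "relative tumor volume is estimated from the MRI using the metric of multiplying the widest tumor diameter with the perpendicular height of the tumor". Change in that measure is a separate exploratory endpoint in Table 1. It has no response threshold and is not linked to the markers.

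**The marker analyses.** Section 15.7 has two. The first is "The Cox model will explore the impact of genetic markers of survival time". The second is "With logistic regression, the association between genetic markers and being a long-term survivor will be explored". No time point defines a long-term survivor. The nearest landmarks are the secondary endpoint in Table 1, "Proportion of patients alive 2 years after PVSRIPO treatment", and the 24-month OS estimate in 15.5; 15.7 refers to neither.

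**The design.** Section 15.9 caps treatment at 12 patients. Section 15.1 says: "All patients who receive PVSRIPO treatment will be included in all safety and efficacy analyses". No untreated or control group is described.

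**The concern.** The endpoint's name and its analysis answer different questions. To call a marker a predictor of response to PVSRIPO is to say that the drug works better in patients who carry it. The analyses ask only whether treated patients with the marker live longer. A marker can do that by tagging a less aggressive tumour. Section 11.1 admits grade III and IV gliomas, ependymoma, medulloblastoma and ATRT, so a marker could simply stand in for grade or histology and still be listed under a heading that speaks of response.

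The logistic analysis raises two practical problems. With so few patients the odds ratio may have no finite estimate. A binary survivor outcome also has no value for a patient censored before the cut-off, and the plan does not say how such a patient is handled. Early censoring is plausible if the cut-off is two years: under 12.4, follow-up after week 48 is at the treating physician's discretion, and data collection from off-study patients is not mandatory.

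**Working it through.** The plan states no power, precision or prevalence figure for the marker analysis, so there is nothing of its own to reproduce. The only documented input is the maximum of 12 patients (15.9). All other inputs below are assumptions for illustration.

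**1. Can a single treated arm separate prognostic from predictive?** Assume constant monthly hazards of death, given as marker-negative / marker-positive.

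| Scenario | Untreated | Treated | Treatment HR, marker− / marker+ |
|---|---|---|---|
| A, purely prognostic | 0.10 / 0.05 | 0.06 / 0.03 | 0.6 / 0.6 |
| B, purely predictive | 0.06 / 0.06 | 0.06 / 0.03 | 1.0 / 0.5 |

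In both, the marker HR among treated patients is 0.03/0.06 = 0.50, and treated 24-month OS is exp(−24 × 0.06) = 23.7% against exp(−24 × 0.03) = 48.7%. The trial observes only the treated column, which is the same in A and B. It therefore cannot tell the two apart, in either direction.

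**2. How many long-term survivors might there be?** If 24-month OS were 10%, 20% or 30%, the expected number is 12 × 0.10 = 1.2, 12 × 0.20 = 2.4 or 12 × 0.30 = 3.6. Counts of 2 to 4 are thus a reasonable range to examine.

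**3. How often does ordinary logistic regression fail for one binary marker?** With s survivors, 12 − s non-survivors and prevalence q independent of survival, the odds ratio has a finite estimate only if both groups contain marker-positive and marker-negative patients. So

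P(fail) = 1 − [1 − q^s − (1−q)^s] × [1 − q^(12−s) − (1−q)^(12−s)].

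Example, s = 3 and q = 0.2: the first bracket is 1 − 0.008 − 0.512 = 0.480, the second is 1 − 0.134 = 0.866 (0.2^9 is negligible), and P(fail) = 1 − 0.480 × 0.866 = 0.58.

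| Survivors | q = 20% | q = 30% | q = 50% |
|---|---|---|---|
| 2 | 71% | 59% | 50% |
| 3 | 58% | 40% | 25% |
| 4 | 51% | 29% | 13% |

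With a single survivor, failure is certain. With 6 the figures are 46%, 22% and 6%.

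**4. A continuous marker.** Section 9.1.4 also lists gene expression. For a continuous marker unrelated to survival, estimation fails only if all survivors lie at one end of the ranking. The chance is 2/C(12, s): 2/66 = 3.0% for s = 2 and 2/220 = 0.9% for s = 3. The problem in step 3 is specific to binary markers.

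**The case against.** The strongest reply is that this is the last of the other exploratory objectives. No alpha, sample size, dose decision or stopping rule depends on it, and 15.7 speaks of exploring associations. The first planned model is a Cox model, which already keeps censored patients, and 12.4 provides for lifelong review of medical records for survival where possible. All of this stands and limits the weight of the point. It does not remove the mismatch between the endpoint's name and its analysis.

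Three stronger readings are tempting, and the documents do not support them.

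- *Response cannot be measured in this trial.* Relative tumour volume is defined in 12.7.3, its change from baseline is an endpoint, and MRI is scheduled at baseline and from week 4 to week 48. Response is undefined for the marker analysis, which is different from unmeasurable. Section 15.6 limits how such imaging can be interpreted but does not make the data absent.
- *Any marker found is prognostic at most.* Step 1 of the working cuts both ways: the same treated-arm data could come from a purely predictive marker. Labelling the results prognostic and not predictive would swap one unsupported claim for another.
- *The marker Cox model ignores grade.* Section 15.7 is silent, but 5.5 and 15.5 call for survival analyses stratified by grade and can be read as covering it. A stratified Cox model in at most 12 patients also loses information, so insisting on one is a trade-off and not a plain correction.

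**Conclusion.** The point holds as a mismatch between what the endpoint is called and what the analyses can show. Response is not defined for the marker objective, the two analyses use survival outcomes, and one treated arm supports only an association with survival after PVSRIPO. These conclusions rest on the text and the design alone.

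The finding on the logistic model rests on assumptions. For a binary marker with 2 to 4 long-term survivors among 12 patients and prevalence from 20% to 50%, the chance of no finite estimate runs from 13% to 71%. Fewer patients treated would change these figures, and a continuous marker is much less affected. The missing cut-off for long-term survivor and the unstated handling of earlier censoring are plain gaps.

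Severity is minor. That a marker would in fact be reported as a response predictor is a risk created by the wording, not something that the documents establish.

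**What to change.** 1. In 5.1, Table 1, 9.1.4 and 15.7, restate the endpoint as *genetic markers associated with overall survival after PVSRIPO (hypothesis-generating; prognostic and predictive effects cannot be separated)*.
2. In 15.7, replace the ordinary logistic model with a Firth-penalised Cox model, or with Kaplan-Meier curves by marker and an exact (permutation) log-rank test. Either keeps censored patients in the analysis.
3. If a long-term-survivor summary is retained, tie it to the 24-month landmark already in Table 1 and 15.5.
4. Show marker results by grade descriptively, without requiring a stratified Cox model.

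No new data are needed. The cost is a more modest claim, a few sentences of text and slightly more analysis work.
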